### 7.3 Comparator: Standard care

Standard of care is variable but reflects a reactive approach to nutritional care. This may include no support, oral nutritional supplements or nasoenteric feeding at anytime point. Clinicians can use PN in the control group, but, as per NICE guidance, not before 5 days post-surgery unless there is pressing clinical need. They may receive interventions such as oral nutritional supplements following surgery, nasogastric feeding, or be permitted to eat, whether or not they have fully recovered gastrointestinal function.

### 7.4 Summary of key steps in the intervention and control arms

The table below summarises the key steps in the intervention and control arms within the TIDiER framework[35]. The intervention arm is the intervention plus standard care.

**Table 2: Key Steps in the intervention and control arms**

|                  | Standard Care   | Intervention (Early Parenteral Nutrition <48 hours post-operatively)  |
|------------------|---|---|
| Why       | Reflects current practice in the NHS; a broadly reactive approach to perioperative nutrition. | Early nutrition may reduce complications and improve clinical outcomes by preventing nutritional deterioration and its sequelae. The gastrointestinal tract is typically non-functional following surgery, so parenteral route is preferred initially |
| Materials | Management in line with local policies for emergency  | Venous access with PICC/CVC   |

|                          |   |  |
|--------------------------|---|--|
|                          | laparotomy recovery and local nutrition policies.   | TPN is required, along with local nutrition policies.  |
| Procedures        | All patients screened with Malnutrition Universal Screening Tool (MUST) or equivalent at admission, and then weekly. Scores of three or more should lead to dietitian review. | Line placed to facilitate feeding, and chest x-ray performed to confirm placement. Baseline blood tests reviewed prior to commencement and key electrolytes replaced prior to commencement of PN or added to PN bag. May also receive B12/Thiamine if high-risk of refeeding syndrome. Energy requirements (Basal metabolic rate plus additional energy needs) are estimated in line with local policies and NICE guidance[25]. Feed is initially commenced at a low rate/volume, building to full energy requirements over a few days, with daily monitoring of electrolytes for the first 7 days. Additional safety tests including liver function monitoring are also performed, as well as monitoring for line sepsis. |
| Who provides      | Oral nutritional supplements can be prescribed at the direction of a nutrition team member, or a member of the surgical team.   | Access is provided by a vascular access specialist (either nurse, anaesthetist, or vascular radiologist depending on local service set up). Assessment of nutritional needs and requirements is led by the nutrition team and prescribed in conjunction with the responsible surgical team.  |
| How               | Provided at an individual level and on a face to face basis.  | Provided at an individual level and on a face to face basis.   |
| Where             | On ward or critical care  | On ward or critical care   |
| When and how much | Nutritional intervention may be provided never, or up to several times a day with oral nutritional supplements. PN may be used  | PN will be provided every 24 hours as per local protocols, until gastrointestinal recovery (passage of flatus/tolerance of diet) and the   |

|                                    |   |   |
|------------------------------------|---|---|
|                                    | at 5 days post-op if required (NICE Clinical Guideline 32)  | participant is able to achieve adequate enteral intake.   |
| Tailoring                   | Route of any nutrition may be adapted depending on the participants drive to eat or ability to reach adequate calorie intake.               | PN dosing may be adjusted daily according to energy requirements and changes in biochemistry.   |
| Planned fidelity assessment | We will record use of nutritional interventions, their type and frequency. We will note if PN is used, and if so, its date of commencement. | We will record use of PN, including number of bags/calories received. We will record other nutritional interventions, their type and frequency. |

## 7.5 Interaction or contraindications

As PN is a form of nutrition, there are no interactions or contraindications.

### 7.5.1 Permitted medication(s)/intervention(s) (including rescue medication)

Patients may take regular or acute medications for any indication as per routine care.

### 7.5.2 Concomitant medication(s)/intervention(s)

No changes to any concomitant medications are required.

### 7.5.3 Prohibited medication(s)/intervention(s)

No medications are prohibited.

### 7.5.4 Clinical deterioration during the trial

Should a participant develop symptoms needing additional or incremental treatment (e.g., steroids or antibiotics) during the trial, they will be managed appropriately by their local team including whether to continue the trial intervention. Participants should still be followed up.

## 7.6 Intervention modification or discontinuation

Participants who develop complications from PN such as cholestasis, significant hyperglycaemia, line sepsis, line occlusion, pneumothorax, or line fracture, may have PN administration paused, reduced, or stopped, as judged by the treating clinical team. These complications are routinely monitored for as part of clinical care.

## **7.7 Continuation of intervention after the trial**

We would expect participants to recover gastrointestinal function following surgery, allowing the intervention to be stopped as intended. A small number of people may develop type III (chronic) intestinal failure and require long term PN at home. Local healthcare contracting exists for this situation and would be outside the scope of this study.

## **7.8 Intervention supply and storage**

Parenteral nutrition is standard NHS stock, and so will be supplied to sites and stored and managed at sites as per local and product requirements.

## **7.9 Adherence**

We will assess adherence in the intervention arm by reporting the percentage of participants who receive PN within 48 hours post-operation. Commencement of the intervention within the 48 hour timeframe is considered adherent and will be monitored centrally.

We will also assess adherence to the control group allocation by monitoring for cross-over to early PN in the control arm. Any participant in the control arm who receives PN within 5 days post-operatively is considered non-adherent.

Adherence to randomised allocation will be assessed in both arms. Sites will be monitored for PN use, and duration of use to identify potential cross-over risks. For the intervention arm, we will record use of PN, including number of bags/calories received. This information will be taken from clinical notes by the research team. We will record other nutritional interventions, their type and frequency. For the control arm, we will record use of nutritional interventions, their type and frequency. If PN is used, we will note its date of commencement and reason for administration. Adherence to intervention relies on commencement of PN within 48 hours post-operation. Adherence to control means no PN used until day 5.

## 8. OUTCOME MEASURES

### 8.1 Internal pilot outcomes

The internal pilot will be conducted across six centres, and we are aiming to recruit 60 participants. At the end of the internal pilot phase, the Trial Management Group (TMG) and Trial Steering Committee (TSC) will review the pilot data against a set of pre-specified Red-Amber-Green (RAG) criteria (Table 3).

**Table 3: Internal Pilot Progression criteria**

| Criterion   | Red
(Stop)
(% complete)                 | Amber
(Modify)
(% complete)                | Green
(Go)
(% complete)               |
|---|---|--|---|
| Participant recruitment (number of open centres achieving their individual target recruitment rate of average 2 participants per month) | <60%  | 60-99%   | 100%  |
| Data completeness for primary outcome (number of expected data points recorded for those randomised)                                    | <90%  | 90-99%   | 100%  |
| Return rate for 90-day questionnaire (EQ-5D-5L, Barthel Index & PRO-diGI gastrointestinal recovery measure)                             | <70%  | 70-99%   | 100%  |
| Intervention delivery (nutritional supplementation to have started within 48 hours)   | <70% in intervention arm; >30% in control arm | 70-99% in intervention arm; 1-30% in control arm | 100% in intervention arm; 0% in control arm |
| Cross over rates between arms   | >10%  | ≤10%   | 0%  |

The following actions will be taken:

- If all criteria are **GREEN (Go)**: progress to main trial; following the pilot phase we would still review trial processes to assess whether any changes could/need to be implemented to improve the trial.

- If any of the criteria are **AMBER (Modify)**: review the trial processes to identify implementable changes. This may include recruiting additional centres and/or retraining centres in trial pathways and procedures. We would discuss with the TSC and funder about the need for a second internal pilot phase to verify resolution of issues, then if progress is satisfactory continue to the main trial.
- If any of the criteria are **RED (Stop)**: abandon the trial if the TSC and Funder feel this the appropriate course of action.

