### 2.1 Internal pilot objectives

The trial includes a 6 month internal pilot phase, which will inform any decision on the continuation of the trial to complete recruitment as planned. The aims of the internal pilot are to assess:

- Recruitment rate (number and rate of participants recruited based on open centres)
- Data completeness for the primary outcome
- Return rate for the 90 day questionnaires
- Intervention delivery within 48 hours
- Cross-over rates between arms

Section 8.1 details the criteria that will determine continuation of the trial beyond the pilot phase.

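### The pilot recruitment criterion counts centres that each reach 2 per month, so with six centres recruiting exactly on target it reads RED slightly more often than not and GREEN only 2-3% of the time

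*Protocol*

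**What the plan says.** Section 2.1 of the protocol lists the first pilot aim as "Recruitment rate (number and rate of participants recruited based on open centres") and sets the length: "The trial includes a 6 month internal pilot phase". Section 8.1 adds: "The internal pilot will be conducted across six centres, and we are aiming to recruit 60 participants".

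Table 3 turns the recruitment aim into a count of centres: "Participant recruitment (number of open centres achieving their individual target recruitment rate of average 2 participants per month"). RED is below 60%, AMBER 60-99% and GREEN 100%. The other four rows are equally strict for GREEN: 100% primary-outcome completeness, 100% return of the 90-day questionnaires, 100% delivery within 48 hours in the intervention arm with 0% in control, and 0% cross-over. The return row is worded "Return rate for 90-day questionnaire (EQ-5D-5L, Barthel Index & PRO-diGI gastrointestinal recovery measure") and states no denominator, whereas the completeness row refers to those randomised.

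The action rules follow the table: "If all criteria are GREEN (Go): progress to main trial". Any AMBER leads to a review of processes and a discussion of a second pilot phase, then to the main trial if progress is satisfactory. Any RED means abandoning the trial only if the TSC and funder judge that appropriate.

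**The concern.** The criterion dichotomises each centre at its own target before anything is added up. A centre whose true rate equals the target reaches it only a little more than half the time, so with six centres the expected number of successes is just over three. Three of six is 50%, which is RED. A pilot recruiting exactly as planned therefore sits on the RED/AMBER border, and GREEN needs all six centres to land on the right side of their own means.

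This also departs from section 2.1, which speaks of participants recruited and not of centres succeeding. A pilot can recruit the planned total and still score badly because the total is spread unevenly. The TSC and funder would then have to explain away a pre-specified RED on a pilot that had met its target.

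**Working it through.** **Inputs.** Six centres and a target of 60 (section 8.1); six months (section 2.1); 2 per centre per month and the 60%/100% limits (Table 3). Assumption, not in the protocol: monthly counts are independent Poisson with the same mean at each centre.

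**The plan's own target.** 6 centres x 6 months x 2 = 72, not 60. The figure of 60 follows from 60/2 = 30 open centre-months (about 5 per centre) or, with 36 centre-months, from 60/36 = 1.67 per month. The protocol states no opening schedule.

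**Table 3 with six centres.** 3/6 = 50%, so 0-3 centres is RED; 4/6 = 67% and 5/6 = 83% are AMBER; only 6/6 is GREEN.

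**On-target pilot.** For a centre open m months at a true rate of 2, p = P(Poisson(2m) >= 2m). The number of centres succeeding is Binomial(6, p); RED = P(at most 3), GREEN = p^6. The pooled alternative is total recruited / (2 x open centre-months) under the same bands, with the total Poisson(12m).

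| Months open | p | RED, per centre | GREEN, per centre | RED, pooled | GREEN, pooled |
|---|---|---|---|---|---|
| 3 | 0.554 | 55.0% | 2.9% | 0.49% | 52.2% |
| 4 | 0.547 | 56.4% | 2.7% | 0.13% | 51.9% |
| 5 | 0.542 | 57.4% | 2.5% | 0.03% | 51.7% |
| 6 | 0.538 | 58.2% | 2.4% | 0.02% | 51.6% |

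Staggered schedules totalling 30 centre-months (for example 6, 6, 5, 5, 4, 4) give RED 57.1-57.4% and GREEN 2.5-2.6%, so staggering reconciles 60 with 2 per month but does not improve the calibration.

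**Sensitivity, six months open.**
- Five centres at rate 2: 3/5 is exactly 60%, hence AMBER. RED is 42.8%, GREEN 4.5%.
- Six centres at other true rates: RED 26.4% and GREEN 11.3% at 2.25; RED 8.1% and GREEN 29.4% at 2.5; RED 1.8% and GREEN 51.7% at 2.75.
- Centres varying around a mean of 2 (gamma-distributed rates): RED 62.5% at a coefficient of variation of 0.2, 66.0% at 0.3 and 72.6% at 0.5.

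**All five rows GREEN.** Suppose each other requirement is met independently with probability 0.99 per participant, for 60 participants on completeness, return and cross-over and 30 on delivery. These are illustrative assumptions. With six centres at rate 2 for six months, P(all GREEN) = 0.0244 x 0.99^210 = 0.3%; with 0.98 it is about 0.04%.

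**The case against.** The strongest reply is that little hangs on the colour. RED leads to a discussion, AMBER is an ordinary route to the main trial, and the committee will see total recruitment anyway because section 2.1 commits to it. That stands. A reader might infer that a healthy trial would be stopped by chance, or that the criteria carry no information. The action rules do not support the first, and the fall in RED from 58% to 8% as the true rate rises from 2 to 2.5 contradicts the second.

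Next, any pass mark set at the true mean is met about half the time, and the RED majority depends on six centres being open. Both are true. The pooled measure is also GREEN only about half the time on target; the difference is that its misses fall in AMBER and almost never in RED.

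Counting centres also has a purpose: it shows whether delivery works site by site before expansion to about 25 hospitals, whereas one strong site can carry a pooled ratio. That is a reason to keep reporting the count, not to let it decide the colour.

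Two stronger readings fail:
- The target of 60 might seem to contradict the rate of 2, with RED at about 93% (1.67 per month over 36 centre-months). That requires every centre to be open for the whole pilot, which the protocol does not say.
- The 9.6% 90-day mortality in section 1.1 might seem to make 100% questionnaire return impossible. The figure 0.904^60 = 0.2% requires all 60 randomised as the denominator and all of them past day 90. Table 3 states neither; with 30 participants past day 90 it would be 0.904^30 = 4.8%.

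**Conclusion.** The point holds as one of calibration and wording. With six centres open 3-6 months at exactly the target rate, the recruitment row reads RED about 55-58% of the time and GREEN 2-3%, under independent Poisson recruitment with equal rates. Between-centre variation makes RED more likely; having five centres open, or a true rate above target, makes it less likely. The row distinguishes good from poor recruitment, but its limits are in the wrong place for the rate it names, and its unit differs from the aim in section 2.1.

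An all-GREEN result is very unlikely, because each of the other rows also allows no shortfall. The consequence is limited to a misleading signal and extra deliberation, since the decision rests with the TSC and funder. The link between 60 participants and 2 per centre per month is unstated rather than shown to be wrong, and the 90-day return row lacks a denominator.

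**What to change.** In Table 3, define the recruitment row as total participants recruited divided by (2 x open centre-months), keeping the bands <60%, 60-99% and >=100%. Report the number of centres reaching 2 per month beside it as a descriptive item, so that a total carried by one strong site is visible.

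In section 8.1, state the open centre-months that give 60 (30 at 2 per month), or change the target or the rate so that they agree. In the return row, name the denominator as participants alive and past day 90 at the time of review.

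Whether GREEN should sit below 100% on the other rows, and at what level, is for the TSC and funder to choose; no particular value follows from the protocol.

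The cost is a wording change to Table 3 and section 8.1, noted by the TSC and funder, preferably before pilot data are reviewed. It uses recruitment and follow-up data the trial already collects and leaves the sample size and main analysis unchanged.

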## 3. TRIAL DESIGN AND SETTING

### 3.1 Trial design

The TONIC trial is a multi-centre, two-arm, parallel group, superiority, individual participant-RCT with 1:1 allocation to early PN or standard nutritional care with an internal pilot and a full economic evaluation. Patients undergoing NELA eligible emergency laparotomy or laparoscopy will be randomised to either early PN started within 48 hours of emergency laparotomy/laparoscopy or standard nutritional care.

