### 7.1 Trial intervention(s)

Participants will be randomised to receive:

- Early PN through central venous catheter (CVC) or PICC, commencing within 48 hours of emergency laparotomy/laparoscopy, with biochemistry monitoring as per NICE Clinical Guideline 32[33]
- Standard nutritional care, which may include no support, oral nutritional supplements or nasoenteric feeding at anytime point. Clinicians can use PN in the control group, but, as per NICE guidance, not before 5 days post-surgery unless there is pressing clinical need.

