#### **14.2.4 Missing data and sensitivity analyses**

Since CCI at hospital discharge can be obtained from the patient's medical history and notes, there should be minimal missing data for the primary outcome. The sample size

calculation has incorporated a potential 5% attrition rate to allow for up to 5% missing data in the primary outcome. If the level of missing data is greater than 5%, then additional sensitivity analyses will be performed to investigate the impact of missing data. Full details of missing data and sensitivity analysis, including on secondary outcomes will be included in the Statistical Analysis Plan.

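### Pilot progression table: the delivery row either scores permitted control-arm feeding as failure or grades early control PN differently from the cross-over row

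*Protocol*

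**What the plan says.** Section 2.1: "The trial includes a 6 month internal pilot phase". Section 8.1: "The internal pilot will be conducted across six centres, and we are aiming to recruit 60 participants". Section 3.1 specifies "1:1 allocation to early PN or standard nutritional care", so each arm has about 30 pilot participants.

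Two rows of Table 3 matter most here.

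- **Delivery row**, "Intervention delivery (nutritional supplementation to have started within 48 hours"). Red is "<70% in intervention arm; >30% in control arm". Amber is 70–99% in the intervention arm and 1–30% in the control arm. Green is 100% and 0%.
- **Cross-over row**, "Cross over rates between arms". Red is above 10%, Amber is up to 10% and Green is 0%. It gives no time window and no denominator.

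Section 7.1 describes the comparator: "Standard nutritional care, which may include no support, oral nutritional supplements or nasoenteric feeding at anytime point". Section 7.3 repeats this. Section 7.9 defines adherence by PN only: started within 48 hours in the intervention arm, and none before day 5 in the control arm. It uses the term cross-over for early PN in controls. Sections 1.2.3, 7.1 and 7.3 also permit control PN before day 5 where there is a pressing clinical need.

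On the consequences, Go needs every row Green. Any Amber leads to review and modification, after which the trial may continue. Any Red leads to stopping only if the steering committee and funder judge that appropriate.

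**The concern.** Table 3 is the pre-specified basis for deciding whether the trial continues after the pilot; sections 14.2 and 16.6 plan no formal interim analysis. Progression criteria are fixed in advance so that a committee need not settle their meaning with the data in view.

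The delivery row does not do that. Taken literally, it counts feeding that the comparator allows, and grades the control arm down for it. Taken to mean PN, it grades early control PN more leniently than the next row grades the same event. Either way the committees would have to decide, after seeing the counts, what the row measures or which row prevails.

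**Working it through.** Table 3 gives no derivation for its thresholds, so there is no threshold calculation to reproduce. The related planning figure is the main sample size (section 14.1: difference 6, SD 27, two-sided 5%, 90% power, 5% attrition):

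n = 2 × (1.960 + 1.2816)² × 27² / 6² = 425.5, so 426 per arm; 426 / 0.95 = 448.4, so 449 per arm, as stated. Nothing below changes it.

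**Reading 1: the row means any nutritional supplementation.** Red needs more than 30% of 30 controls, that is 10 or more (10/30 = 33%). The protocol gives no rate of oral or enteral feeding in the first 48 hours, so the rates below are assumptions.

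| Assumed true rate | P(10 or more of 30) |
|---|---|
| 10% | 0.05% |
| 15% | 1.0% |
| 20% | 6% |
| 30% | 41% |
| 40% | 82% |
| 50% | 98% |

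A single such control (1/30 = 3.3%) already removes Green.

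**Reading 2: the row means PN.** Any control who starts PN within 48 hours has also had PN before day 5, and so is a cross-over under section 7.9. The cross-over count is therefore at least as large as the control count on the delivery row.

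| Controls with PN within 48 h | Share of 30 | Delivery row | Cross-over row, of 30 | Cross-over row, of 60 |
|---|---|---|---|---|
| 3 | 10% | Amber | Amber | Amber (5%) |
| 4 | 13% | Amber | Red | Amber (6.7%) |
| 6 | 20% | Amber | Red | Amber (10%) |
| 7 | 23% | Amber | Red | Red (11.7%) |
| 9 | 30% | Amber | Red | Red (15%) |
| 10 | 33% | Red | Red | Red (16.7%) |

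The cross-over column assumes no other cross-overs; later ones, between 48 hours and day 5, could only raise it. The rows disagree at 4–9 controls with a per-arm denominator and at 7–9 with a pooled one.

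**Denominator of the 90-day return row.** The table states none. The assessment window closes at day 97 (90 + 7). If 60 participants enter evenly over 6 months (182.6 days), the share past day 97 at the end is (182.6 − 97)/182.6 = 47%, about 28 people. With a linear ramp it is 0.47² = 22%, about 13. Both recruitment patterns are assumptions. Dividing by all 60 at that date would cap the return rate at about 47%, under the 70% Red line. The table does not say that it would be done so, but it should exclude it.

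**Green for primary-outcome completeness.** Section 14.2.4 says the "calculation has incorporated a potential 5% attrition rate to allow for up to 5% missing data in the primary outcome". At exactly 95% true completeness, P(60 of 60) = 0.95⁶⁰ = 4.6%; at 99% it is 0.99⁶⁰ = 55%.

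**The case against.** The protocol's own usage favours PN. The row is titled as intervention delivery, section 2.1 lists it so, and sections 1.2 and 14.2.1 use nutritional supplementation as a name for the randomised treatment. Section 1.2.2 says controls typically receive nothing in the first 48 hours. This stands: the literal reading is probably loose wording, and at a 20% feeding rate it would produce Red only 6% of the time. But the PN reading leads straight to the conflict with the cross-over row.

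It can also be said that any Red criterion triggers the Red action, so the stricter row governs. That settles the label, but makes the 11–30% part of the delivery row's control-arm Amber band ineffective under a per-arm denominator. It still leaves the denominator and window open.

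Several stronger inferences are tempting and not supported.

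- That both faults occur together: they need alternative readings of one row.
- That the table cannot yield a decision: Red is discretionary and Amber allows continuation.
- That a Green of 100% or 0% contradicts the plan. Section 14.2.1 expects some switching, but a strict bar that makes Amber usual is a choice. The 5% is an upper allowance, with minimal missing data expected.
- That undelivered PN in the intervention arm is cross-over: section 7.9 treats it as non-adherence.
- That the trial would lose stated power at the Amber limits: this needs 6 points to be the effect under full adherence, which the protocol does not say, and the estimand follows treatment policy.

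**Conclusion.** The point holds. On its wording, the delivery row grades permitted control feeding as failure. On the PN reading, the same early control PN is Amber on one row and Red on the next, for 4–9 of 30 controls per arm or 7–9 if pooled over 60. These counts assume 30 participants per arm; the chances of Red under the literal reading rest on assumed feeding rates and are illustrative only.

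The consequence is an ambiguous progression decision. The estimand, primary analysis, error rate and sample size are untouched.

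**What to change.** Amend Table 3 before the pilot review, since a change afterwards would be informed by the data.

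1. Delivery row: replace nutritional supplementation with PN and apply it to the intervention arm only.
2. Cross-over row: grade control-arm PN here only, with the section 7.9 window (PN before day 5) and control participants as the stated denominator. Sections 1.2.3, 7.1 and 7.3, which permit earlier control PN for pressing clinical need, must be reconciled with section 7.9, so that it is clear whether those starts count. Without a window, the row would count PN that the protocol allows from day 5.
3. 90-day return row: state that the denominator is questionnaires due, meaning participants past the day-90 window.
4. Optional: the steering committee and funder may set Green for primary-outcome completeness at 95% or more, in line with the attrition allowance. The document offers no source for other Green cut-offs, so those are theirs to choose.

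The cost is a one-table protocol amendment agreed with the steering committee and funder. Recruitment, treatment and sample size do not change.
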